#### **9.4.7.3. Vital Signs**

Descriptive statistics will be provided for the vital signs measurements by scheduled time of evaluation (including the EOT visit), as well as for the change from baseline. In addition, the change from baseline will be presented for the maximum and minimum post-treatment values.

#### **9.4.7.4. ECG**

Electrocardiogram parameters (PR, RR, QRS, QT, QTcB, and QTcF) will be summarized using descriptive statistics for actual values and for changes from baseline by scheduled time of evaluation, including the EOT Visit and the maximum post-treatment value. Both scheduled and

unscheduled post-treatment values will be considered for summaries of the maximum post-treatment values. The corrected QT intervals using Bazett's and Fridericia's formula will be calculated as follows:  $QT_cB = QT/(RR)^{1/2}$  and  $QT_cF = QT/(RR)^{1/3}$ .

The incidence of notable ECG changes in maximum absolute QT,  $QT_cF$ , and  $QT_cB$  over all post-treatment evaluations will be summarized using the following intervals:

- New  $> 450$  and  $\leq 480$  ms;
- New  $> 480$  and  $\leq 500$  ms;
- New  $> 500$  ms.

The incidence of notable ECG changes in QT,  $QT_cF$ , and  $QT_cB$  maximum changes from baseline over all post-treatment evaluations will be summarized with the following intervals:

1. 30 and  $\leq 60$  ms;
2.  $> 60$  ms;

All triplicate ECG measurements at a particular timepoint will be averaged prior to analysis and summarization.

#### 9.4.8. Dosing and Extent of Exposure

The following items of DS-1594b administration will be summarized.

1. Treatment duration (day)  
= Last dose date – First dose date + 1
2. Study duration (day)  
= Date of the Follow-up visit – First dose date + 1
3. Total amount of DS-1594b taken (mg)
4. Dose intensity (mg)  
= Total amount of doses taken / (Treatment duration)
5. Relative dose intensity (%)  
= Actual Dose intensity / Planned dose intensity \* 100

In addition, the total number of cycles initiated will be summarized using descriptive statistics.

In Phase 2, DS-1594b dosing status will be summarized to show the number and percentage of subjects with and without dose reductions or interruptions. For subjects with dose reductions or interruptions, the reasons will be provided. A listing of dose escalation subjects with dose reductions or interruptions will be provided.

For the combination-treatment cohorts C & D in Phase 2, the exposure of the combination drugs azacitidine and venetoclax, and mini-HCVD will be summarized separately.

All study drug administration data will be listed by subject by study Phase.

#### 9.4.9. PK Analyses

DS-1594b PK parameters will be determined using non-compartmental method(s) and fitting of the actual values to a population PK model. The single-dose dose and multiple dose PK parameters listed in Section 8.4 will be estimated and reported, as appropriate.

Descriptive statistics (n, mean, SD, CV%, median, minimum, and maximum) will be performed on all PK parameters by cohort and study day. Geometric means and geometric CV% will be presented for Cmax, AUClast, AUCinf, AUCtau, Ctrough, Cavg, CL/F, CLss/F, Vz/F and AR. Medians and ranges will be presented for Tmax, Tlast, t1/2, and t1/2,ar.

Descriptive statistics (n, mean, SD, median, geometric mean, CV%, geometric CV%, minimum, and maximum) will be presented for plasma concentrations by cohort.

A graphical presentation of the plasma concentration profiles will also be provided by cohort using the arithmetic mean (+/- SD) and geometric mean values at each scheduled time point for full PK collection profile on Cycle 1 Day 1, Cycle 1 Day 8, Cycle 1 Day 15 (food effect sub-study), Cycle 1 Day 18 (DDI sub-study) and Cycle 2 Day 10 (DDI sub-study). The trough concentration -time profile will also be plotted by cohort.

Concentration values below the lower limit of quantitation (LLOQ) will be displayed in listings as zero with a flag and handled as zero in any calculations of summary statistics but handled as missing for the calculation of the geometric means and their CV%. Any missing PK parameter data will not to be imputed.

##### 9.4.9.1. Food Effect Sub-Study

The effect of meal on the steady-state PK of DS-1594b will be evaluated in the food effect sub-study when:

- DS-1594b is administered orally twice daily or daily with a standard meal from Cycle 1 Day 1 to Cycle 1 Day 8.
- DS-1594b is administered orally twice daily or daily under fasting condition from Cycle 1 Day 9 to Cycle 1 Day 18.

The analysis will consider the primary PK parameters AUCtau and Cmax of DS-1594b on Cycle 1 Day 8 and Cycle 1 Day 18. A mixed-effects model will be used with treatment period (fed vs. fasting) as a fixed effect and subject as a random effect on log-transformed PK parameter data, and the results will be presented at original scale after back-transformation. The geometric mean of DS-1594b PK parameters (as estimated by the mixed effect model) will be calculated and the geometric mean ratio of DS-1594b PK parameters (Cycle 1 Day 18 relative to Cycle 1 Day 8) will be reported with 90% CIs.

##### 9.4.9.2. DDI Sub-Study

The effect of multiple doses of strong CYP3A inhibitor on the steady-state PK of DS-1594b will be evaluated in the DDI sub-study when:

- DS-1594b is administered orally twice daily or daily alone from Cycle 1 Day 1 to Cycle 1 Day 8.

- DS-1594b is administered oral twice daily or daily with strong CYP3A inhibitor (posaconazole or vericonazole) from Cycle 1 Day 9 to Cycle 1 Day 18 (or Cycle 2 Day 1 to Cycle 2 Day 10).

The analysis will consider the primary PK parameters AUCtau and Cmax of DS-1594b on Cycle 1 Day 8 and Cycle 1 Day 18 (or Cycle 2 Day 10). A mixed-effects model will be used with treatment period (with CYP3A inhibitor vs. without CYP3A inhibitor) as a fixed effect and subject as a random effect on log-transformed PK parameter data, and the results will be presented at original scale after back-transformation. The geometric mean of DS-1594b PK parameters (as estimated by the mixed effect model) will be calculated and the geometric mean ratio of DS-1594b PK parameters (Cycle 1 Day 18 (or Cycle 2 Day 10) relative to Cycle 1 Day 8) will be reported with 90% CIs.

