### 3.2.3.2. Sub-study Design

Following dosing in Phase 1 Dose Escalation and MTD declaration, approximately 12 additional subjects will be enrolled into a drug-drug interaction (DDI) sub-study within the Phase 1 portion of the study at a predetermined dose level (at least 50% below the RP2D, as recommended by the SRC) to assess the effect of multiple doses of antifungal agents (i.e. posaconazole [N ~ 6], voriconazole [N ~ 6]) that are strong CYP3A inhibitors, on the steady-state PK of DS-1594b. Based on preliminary assessment using physiologic-based modeling, the magnitude of PK increase of DS-1594b ranges from 30% (with posaconazole) to 2-fold (with voriconazole).

This estimate will be further assessed based on emerging clinical and nonclinical data and the information will be provided to the SRC for consideration in dose selection. Nonetheless, the dose will be at least 50% below the declared RP2D. These subjects can be the same subjects included in the Phase 1 expansion for RP2D determination.

This DDI sub-study is a single sequence, crossover design. Enrollment will complete on the posaconazole sub-study before enrollment will begin on the voriconazole sub-study. Subjects will receive twice-daily or daily oral dosing of DS-1594b alone at the assigned dose from Cycle 1 Day 1 to Cycle 1 Day 8. On Cycle 1 Day 9 to Cycle 1 Day 18, subjects will receive the same assigned DS-1594b dose with either (a) 300 mg oral posaconazole twice on Cycle 1 Day 9 and once daily on Cycle 1 Day 10 to Cycle 1 Day 18 or (b) 400 mg oral voriconazole twice on Cycle 1 Day 9 and 200 mg twice daily from Cycle 1 Day 10 to Cycle 1 Day 18.

The anti-fungal agents are planned to be given for 10 consecutive days as stated above to ensure steady-state is reached in order to maximize inhibitory effect on CYP3A-mediated metabolism of DS-1594b. After completion of the sub-study (Cycle 1 Day 18 is the last day of the sub-study), subjects will continue with DS-1594b dosing alone starting on Cycle 1 Day 19. PK sampling timepoints of DS-1594b are outlined in [Table 17](#)[Table 17](#).

Formatted: C-Hyperlink

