**Note:** If the use of posaconazole is essential for subject care during the dose escalation phase (i.e. prior to MTD/RP2D declaration), the subject can enter the DDI sub-study sooner, starting from the third dose escalation cohort. Voriconazole is not allowed as DDI perpetrator prior to MTD declaration given it is a more potent CYP3A inhibitor compared to posaconazole. To avoid interference with the DLT evaluation period (first 28-day cycle), subjects will receive oral twice daily or daily dosing of DS-1594b alone at the assigned dose for the entire Cycle 1. Starting on Cycle 2 Day 1 to Cycle 2 Day 10, subjects will receive either the same assigned DS-1594b dose provided that dose level has been declared safe from the DLT evaluation, or at one dose level lower with 300 mg oral posaconazole twice on Cycle 2 Day 1 and once daily on Cycle 2 Day 2 to Cycle 2 Day 10. After completion of the sub-study (Cycle 2 Day 10 is the last day of the sub-study), subjects will continue with DS-1594b dosing alone starting on Cycle 2 Day 11. PK sampling timepoints of DS-1594b for these subjects are outlined in [Table 18](#)[Table 18](#). These subjects will contribute to the overall sample size of ~ 12 for DDI sub-study.

Formatted: C-Hyperlink, Font: Italic

The entry criteria for subjects in DDI sub-study will be the same as all other subjects, except for additional concomitant medications restrictions for CYP3A modulators and gastric reducing agents (see Section 4.2 ).

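### The drug-interaction model does not adjust for DS-1594b dose, although early posaconazole subjects may take a lower dose with the azole than without it, which biases the posaconazole ratio downward

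*Combined protocol and SAP*

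**What the plan says.** Section 9.4.9.2 sets the outcome and the model. "The analysis will consider the primary PK parameters AUCtau and Cmax of DS-1594b" on Cycle 1 Day 8 and on the co-administration day. The model has "treatment period (with CYP3A inhibitor vs. without CYP3A inhibitor) as a fixed effect" and "subject as a random effect on log-transformed PK parameter data". The contrast is "Cycle 1 Day 18 (or Cycle 2 Day 10) relative to Cycle 1 Day 8) will be reported with 90% CIs". The inhibitor period is described once for both azoles, "with strong CYP3A inhibitor (posaconazole or vericonazole"; there is no azole term and no statement that results are given by azole.

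Section 3.2.3.2 describes two routes into the sub-study.

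- After MTD declaration, DS-1594b is unchanged across periods: "subjects will receive the same assigned DS-1594b dose with either" posaconazole or voriconazole.
- Before MTD declaration, from the third escalation cohort and with posaconazole only, subjects take DS-1594b alone in Cycle 1. In Cycle 2 they take either the same dose, if it has been declared safe, "or at one dose level lower with 300 mg oral posaconazole twice on Cycle 2 Day 1". These subjects count toward the total of about 12.

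The same section plans about six subjects per azole, enrols the azoles one after the other, and cites modelling in which the exposure increase "ranges from 30% (with posaconazole) to 2-fold (with voriconazole".

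Section 3.2.3.3 requires the assigned dose on both PK days and replaces subjects who are not evaluable. Sections 8.4 and 9.4.9 derive and summarise CLss/F, but it is not an outcome of the interaction model.

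**The concern.** A single-sequence comparison treats each subject as his or her own control. That works if the only planned difference between the two PK days is the azole. For a pre-MTD subject who takes the lower-dose option, two things change together: posaconazole is added and the DS-1594b dose falls. The within/without-inhibitor factor changes on the same day as the dose, so the model cannot separate them. The random subject effect does not help, because the change is within subject.

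The bias understates the interaction. The sub-study is meant to identify a DS-1594b regimen that can be given with antifungals, possibly extending to other strong CYP3A inhibitors (Section 3.2.3.1). Section 5.6.4 restricts those inhibitors until the assessment is done. An understated ratio would misinform that decision.

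A second, separate gap is that one inhibitor effect is written for two azoles that the protocol expects to differ. If the model were run literally on all 12 subjects, its ratio would describe neither drug.

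**Working it through.** **Inputs from the documents**

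- Expected ratios: 1.3 for posaconazole and 2.0 for voriconazole (Section 3.2.3.2). They come from physiologic-based modelling whose inputs are not given, so they cannot be reproduced. They are used here as the true ratios for exposure.
- Sample: about 6 per azole; 6 + 6 = 12 agrees with the stated total.
- Only posaconazole subjects can be on a reduced dose, because voriconazole is not allowed before MTD declaration.

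**Assumptions**

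- d is the lower dose divided by the original dose. The dose ladder is in Figure 1, which is not shown, so a range is used. The intra-patient escalation example in Section 6.9 (50 and 70 mg BID, d = 50/70 = 0.714) is included only for scale.
- k is the number of the six posaconazole subjects on the lower dose. The documents give no figure.
- Exposure is proportional to dose over one step.

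**Formulas**

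With two complete records per subject, the model's ratio is the exponential of the mean within-subject log ratio. A mixed model fitted to simulated data for 12 subjects agreed with that calculation (1.382 by both routes). Hence, ignoring sampling error:

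- posaconazole-only ratio = 1.3 × d^(k/6)
- pooled 6+6 ratio = exp[(6 ln 1.3 + 6 ln 2.0 + k ln d)/12]

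**Results without dose normalisation**

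| d | Posaconazole only, k = 2 | k = 3 | k = 6 | Pooled 6+6, k = 6 |
|---|---|---|---|---|
| 0.75 | 1.18 | 1.13 | 0.98 | 1.40 |
| 0.714 | 1.16 | 1.10 | 0.93 | 1.36 |
| 0.667 | 1.14 | 1.06 | 0.87 | 1.32 |
| 0.5 | 1.03 | 0.92 | 0.65 | 1.14 |
| 0.333 | 0.90 | 0.75 | 0.43 | 0.93 |

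**Where the ratio crosses 1**

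- Posaconazole only: d < 1.3^(−6/k). This is 0.769 for k = 6 (a cut above 23%), 0.592 for k = 3 and 0.455 for k = 2.
- Pooled 6+6: d < (1.3 × 2.0)^(−6/k). This is 1/2.6 = 0.385 for k = 6 and 0.148 for k = 3.

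**Pooling with no dose reduction**

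√(1.3 × 2.0) = 1.61. That overstates the posaconazole ratio and understates the voriconazole ratio.

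**After dose normalisation and separate fits**

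Dividing each exposure by the dose taken removes d, so the expected ratios are 1.30 and 2.00 for any d and k, under proportionality.

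**The case against.** Four arguments tell against the concern.

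1. *Reduced-dose subjects may be excluded already.* Section 3.2.3.2 contrasts the same assigned dose with one level lower, so the assigned dose may mean the Cycle 1 dose. Section 3.2.3.3 then requires the assigned dose on Cycle 2 Day 10, which would make these subjects non-evaluable. Against this, Section 3.2.3.2 says that early entrants contribute to the total, and a lower level given for Cycle 2 can equally be called assigned. The text is ambiguous and does not clearly remove them.

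2. *Few subjects may be affected.* Early entry is an exception, for subjects in whom posaconazole is essential, and they may stay on the same dose. This stands. The 0.65 to 0.87 range is the case in which all six are reduced.

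3. *Dose-adjusted results are planned elsewhere.* CLss/F is dose over AUCtau, and a population PK model is planned. A false decrease in AUCtau would look odd beside them. But CLss/F is only described, carries no planned ratio or interval, and says nothing about Cmax.

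4. *The azoles may well be analysed separately.* Section 3.2.3.2 speaks of a posaconazole and a voriconazole sub-study in sequence, and Section 3.2.4.3 refers to each group of the interaction sub-study. This stands too. A reader might infer from Section 9.4.9.2 that the plan pools them, but that is inferred from silence.

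A reader might also infer that the two gaps together make the reported ratio point the wrong way. They do not. Pooling pulls the ratio up, because the voriconazole subjects are unaffected. A pooled fit with all six posaconazole subjects at half dose still gives 1.14.

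**Conclusion.** The dose confounding is real and the model as written has no safeguard against it. It affects the posaconazole ratio only, through pre-MTD subjects who take the lower-dose option, and always in the direction of understating the interaction. Under dose-proportional exposure and a true ratio of 1.30, the size runs from negligible (no one reduced) through 1.03 (two of six halved) and 0.92 (three of six halved) to 0.65 (all six halved). A real increase can therefore appear as a decrease in a posaconazole-only estimate, but only with a large enough step and enough subjects reduced. In a pooled fit it needs a lower dose below about 0.385 of the original in all six.

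The handling of the two azoles is a gap in the text, not a demonstrated error; the figure of 1.61 applies only if the model is run literally on all subjects.

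This is a should-fix. The interaction assessment is a secondary PK objective (Table 2), reported as an estimate with a 90% interval and without a decision rule in Section 9.4.9.2, and no primary endpoint depends on it.

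**What to change.** In Section 9.4.9.2:

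- Analyse AUCtau and Cmax divided by the DS-1594b dose taken on that PK day, and state that this assumes dose-proportional exposure over one dose level.
- Add a sensitivity analysis limited to subjects on the same DS-1594b dose in both periods.
- Fit posaconazole and voriconazole separately (or as distinct levels of one factor) and report a ratio with 90% CI for each.

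The meaning of assigned dose in Section 3.2.3.3 and the lower-dose option in Section 3.2.3.2 must be reconciled, so that it is clear whether reduced-dose subjects are evaluable.

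The model changes are SAP wording, with no extra samples, visits or subjects. There are two costs. Proportionality is not guaranteed: Section 2.4.2 reports that DS-1594b is both metabolised by CYP3A and a time-dependent inhibitor of it in vitro. The escalation PK data can be used to check it. And each azole's interval rests on about six subjects, fewer in the same-dose analysis, so the intervals may be wide.

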#### **9.4.10. PK/PD Analyses**

Additional exploratory analyses may be conducted to identify possible relationships of appropriate observed or population PK-derived PK parameters with clinical efficacy, safety variables, biomarkers, or dosing change as appropriate.

To assess the effect of DS-1594b on the QT interval, QTc changes from baseline will be plotted against the time-matched PK concentration, for each QTc parameter. In addition, a linear mixed effects model may be used to analyze changes from baseline QTc versus DS-1594b PK concentrations, including covariates such as baseline QTc, age, gender, race. Details will be described in a separate modeling plan.

## 10. APPENDICES

**Table 28: List of Prohibited QT Prolongation Drugs**

Prohibited medications causing QTc prolongation			
Antiarrhythmic:	Anticancer:	Antibiotic:	Antianginal:
amiodarone	arsenic trioxide	azithromycin	bepridil
disopyramide	vandetanib	clarithromycin*	
dofetilide	oxaliplatin	erythromycin*	Antipsychotic:
flecainide	Antihistamine:	moxifloxacin	chlorpromazine
ibutilide	astemizole*	sparfloxacin	haloperidol*
procainamide	terfenadine*	levofloxacin	mesoridazine
quinidine*		ciprofloxacin	pimozide
sotalol	Antimalarial:	grepafloxacin	thioridazine
dronedarone*	chloroquine	Antinausea:	sulpiride
	halofantrine	domperidone	levomepromazine
Antilipemic:	hydroxychloroquine	droperidol	Opiate agonist:
probucol		ondansetron	levomethadyl
Antidepressant:		GI stimulant:	methadone
citalopram	Anti-infective:	cisapride*	cocaine
escitalopram	pentamidine		Other:
			anagrelide
			sevoflurane
			cilostazol
			donepezil
			papaverine
			propofol

Note: \*CYP3A substrate

Source: The most updated list is available on website <https://www.crediblemeds.org/healthcare-providers/drug-list>

**Table 29: Prohibited Medications That Are Strong Inhibitors or Inducers of CYP3A, or CYP3A/P-Gp and CYP2C19 Substrates with Narrow Therapeutic Indices**

CYP3A4/5 substrates and/or P-gp substrates with narrow therapeutic index			
astemizole*	diergotamine	pimozide*	alfentanil
cisapride*	ergotamine	quinidine*	terfenadine*
cyclosporine	fentanyl	tacrolimus	sirolimus
digoxin	paclitaxel		
CYP2C19 substrates with narrow therapeutic index			
(S)-mephénytoin			
Strong CYP3A inhibitors			
Macrolide antibiotics:	Antivirals:	Antifungals:	Others:
clarithromycin**	indinavir	itraconazole**	conivaptan
telithromycin	lopinavir/ritonavir	ketoconazole	
troleandomycin	nelfinavir	posaconazole	mibefradil
	ritonavir**	voriconazole	nefazodone
	indinavir/ritonavir**		
	saquinavir		
	saquinavir/ritonavir**		
	telaprevir**		
	tipranavir/ritonavir**		
	danoprevir/ritonavir**		
	elvitegravir/ritonavir**		
	boceprevir		
	cobicistat		
Strong CYP3A/5 inducers			
avasimibe	carbamazepine	phenobarbital	phenytoin
rifabutin	rifampin	St. John's wort	mitotane

\* Compounds known to increase QTc interval that are also primarily metabolized by CYP3A4/5.

\*\* Compounds known to have P-gp inhibitory effect

Reference:

University of Washington's Drug Interaction Database

<http://www.fda.gov/Drugs/DevelopmentApprovalProcess/DevelopmentResources/DrugInteractionsLabeling/ucm093664.htm#4>

**Table 30: List of medications to be used with caution**

Moderate CYP3A4/5 inhibitors*			
netupitant	darunavir	grapefruit juice	crizotinib
atazanavir/ritonavir	darunavir/ritonavir	aprepitant	tofisopam
amprenavir	diltiazem	casopitant	lomitapide
atazanavir	verapamil	cimetidine	
	imatinib	nilotinib	
Moderate CYP3A4/5 inducers*			
bosentan	efavirenz	etravirine	modafinil
nafcillin	lersivirine	talviraline	tipranavir
	lopinavir		
P-gp inhibitors (not strong CYP3A inhibitors)			
carvedilol	lapatinib	propafenone	ranolazine
verapamil			
BCRP substrates			
atorvastatin	daunorubicin	doxorubicin	imatinib
methotrexate	mitoxantrone	pitavastatin	rosuvastatin
SN-38 (irinotecan)	ethinyl estradiol	simvastatin	sulfasalazine
sofosbuvir	topotecan		
OCT1/2 substrates			
metformin	phenformin	6-beta-hydroxycortisol	amantadine
carboplatin	cisplatin	histamine	lamivudine
linagliptin	oxaliplatin	oxybutynin	picoplatin
pramsorafenib	tropisetron	trospium	varenicline
umeclidinium			
P-gp substrates			
aliskiren	ambrisentan	atorvastatin	azithromycin
cerivastatin	colchicine	cyclosporine	dabigatran
docetaxel	domperidone	doxorubicin	fexofenadine
lapatinib	linezolid	loperamide	maraviroc
nevirapine	proguanil	ritonavir	ranolazine
simvastatin	sofosbuvir	ticagrelor	voclosporin

Protocol 2020-0946  
20 Aug 2021  
Version 5.0

**Table 30: List of medications to be used with caution (Continued)**

**Gastric reducing agents (proton pump inhibitors)**

esomeprazole	lansoprazole	omeprazole	pantoprazole
rabeprozole			

\*Subjects enrolled in DDI and food effect sub-studies will have moderate CYP3A inhibitors and inducers prohibited (see [Appendix Table 31](#)[Table 31](#)).

Formatted: C-Hyperlink

References:

University of Washington's Drug Interaction Database  
<http://www.fda.gov/Drugs/DevelopmentApprovalProcess/DevelopmentResources/DrugInteractionsLabeling/ucm093664.htm#4>

**Table 31: Additional Prohibited Medications for Subjects Enrolled in DDI and Food Effect Sub-Studies**

Moderate CYP3A4/5 inhibitors			
netupitant	darunavir	grapefruit juice	crizotinib
atazanavir/ritonavir	darunavir/ritonavir	aprepitant	tofisopam
amprenavir	diltiazem	casopitant	lomitapide
atazanavir	verapamil	cimetidine	
fluconazole	imatinib	nilotinib	
Moderate CYP3A4/5 inducers			
bosentan	efavirenz	etravirine	modafinil
naftilin	lersivirine	talviraline	tipranavir
	lopinavir		
Gastric reducing agents (proton pump inhibitors)			
esomeprazole	lansoprazole	omeprazole	pantoprazole
rabeprazole			

References:  
University of Washington's Drug Interaction Database  
<http://www.fda.gov/Drugs/DevelopmentApprovalProcess/DevelopmentResources/DrugInteractionsLabeling/ucm093664.htm#4>

